Safety will be assessed through analyses of treatment emergent adverse events (TEAEs), as well as baseline and pre- and post-infusion ECGs, physical examinations, vital signs measurements, and laboratory measurements (including clinical chemistry, hematology and urinalysis). Serious adverse events (SAEs) and non-SAEs will be collected and reported until 16 weeks following the last administration of iobenguane I 131. Adverse events of special interest (AESIs), including radiation toxicity, reported beyond 16 weeks after the last therapeutic dose of study drug will be collected during the 12 month assessment period and until completion of the follow up period.

After the 12-month assessment, subjects enter long-term follow-up and remain in follow-up for a total of 5 years following the first therapeutic dose. Subjects will be followed for AESIs and overall survival for 5 years post-treatment. In years 2-5 post-treatment (or until a subject experiences disease progression, start of another anticancer therapy or death), data on tumor response, tumor markers and clinical benefit (to month 18 only) will be collected through assessments provided by institutional standard of care.

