7.4.1. Primary Analysis: Reduction in Use of Antihypertensive Medication

The primary endpoint for this trial is the proportion of study subjects with a reduction (including discontinuation) of all antihypertensive medication by at least 50% for at least six months or two cycles of iobenguane I 131. The 50% reduction is determined separately for each baseline medication, based on the total daily dose of the antihypertensive medication(s) on the day of the first therapeutic dose.

A benefit duration period is measured by maximum duration as follows. The benefit duration period commences when the subject's medication is reduced to a level below 50% of baseline, and continues until the subject's medication rises above 50% of baseline, until the onset of a new antihypertensive medication of >14 days' duration, or to the last subject date as described in section 7.4.2, Primary Endpoint Calculation. A benefit duration period must begin during the 12-Month Efficacy Phase but may end during the Long-term Follow-up Phase. If the subject discontinues participation in the study before the Month 12 efficacy evaluation, the last date for calculation of the duration of benefit is the date of termination in the study.

For purposes of illustration, the following examples are provided (Month refers to the number of 28-day months after the first Therapeutic Dose).

- Example 1: A subject experiences the clinical benefit from the beginning of Month 2 to the beginning of Month 4, and then again from the beginning of Month 5 to the beginning of Month 12. Since the maximum duration of the benefit was 7 months, the subject is considered a success on the primary endpoint.
- Example 2: A subject experiences the clinical benefit from the beginning of Month 2 to the beginning of Month 4, and then again from the beginning of Month 6 to the beginning of

Month 11. Even though the subject experienced the clinical benefit for a total of 7 months, the maximum duration of the benefit was only 5 months, so the subject is considered a failure on the primary endpoint.

- Example 3: A subject experiences the benefit from the beginning of Month 2 to the beginning of Month 9. At Month 10, the subject receives another anticancer treatment and is discontinued from the study. Since the maximum duration of the benefit was 7 months, prior to discontinuation, the subject is considered a success on the primary endpoint.

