5. A long-term (i.e., duration > 14 days) increase in dose over the baseline dose of an existing antihypertensive medication regimen after receiving a therapeutic dose will not disqualify a subject from being able to achieve the primary endpoint if all antihypertensive medications are reduced to a level of 50% or below the baseline dose for at least six consecutive months in duration, since the increase may have been made before a tumor response was obtained. The introduction of a new antihypertensive medication with a duration of >14 days will be considered as the end of a benefit duration period. The start date for the duration of response is the date that the last antihypertensive medication is reduced to the level of 50% or below the baseline dose.
6. The introduction of an antihypertensive medication regimen or increase in existing antihypertensive medication regimen that occurs after the subject has already met the primary endpoint (i.e., had a $\geq 50\%$ reduction of all antihypertensive medications for at least six consecutive months) will not disqualify the subject from achieving the primary endpoint.

Calculation of Duration of Response

The six-month duration of the primary endpoint response begins on the date during the 12-Month Efficacy Phase when all baseline antihypertensive medications have been reduced by at least 50% and any new medications are discontinued (the date post-therapeutic dosing when the reduction of the last antihypertensive medication reduced by at least 50% or the new medication is discontinued) and ends once six consecutive months (i.e., 168 days) duration of sustained $\geq 50\%$ reduction has been achieved, regardless of the phase of the study during which the end date of the response occurs (i.e., 12-Month Efficacy Phase vs. Long-Term Follow-Up Phase).

The end date for which the duration of the $\geq 50\%$ reduction of all antihypertensive medications is determined as the earlier of:

- a. the date that the subject no longer meets the criteria of having a $\geq 50\%$ reduction of all baseline antihypertensive medications (i.e., the starting date of a new long-term continuing antihypertensive medication or a dose change in an existing regimen of antihypertensive medication that exceeds the $\geq 50\%$ reduction of the baseline dose that is greater than 14 days in duration and continues without a reduction to the $\geq 50\%$ level)

OR

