- b. the date of the subject's last applicable recorded study-related disposition date. If the subject has discontinued the study prior to the end of the 12-Month Efficacy Phase due to any of the following reasons:
- Withdrew consent
 - Was lost to follow-up
 - Death
 - Withdrew due to progressive disease
 - Received other anticancer therapy
 - Experienced an adverse event resulting in study discontinuation

The last participation date is the corresponding disposition date within the 12-Month Efficacy Phase (i.e., date that the subject withdrew consent, was lost to follow-up, died, withdrew due to disease progression, received other anticancer therapy, or experienced an adverse event resulting in study discontinuation).

If the subject has completed the 12-Month Efficacy Phase but continues to meet the criteria of having a $\geq 50\%$ reduction of all antihypertensive medications, the last applicable disposition date would be the long-term follow-up completion/discontinuation date.

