7.6. Procedures for Handling Missing, Unused and Spurious Data

All available efficacy and safety data will be included in data listings and tabulations. No imputation of values for missing data will be performed in the primary analysis.

Subjects who receive the study agent but have no follow-up for safety will not be included when computing incidence of AEs or laboratory toxicities, because their inclusion would dilute the percentages.

Data that are potentially spurious or erroneous will be examined using standard data management operating procedures, prior to database lock and statistical analysis.

Incomplete medication start and end dates are handled as follows: a missing start month is imputed as June and a missing end month is imputed as December. A missing start and end date are imputed as the last day of the month. If only the year is provided, the start date would be imputed as June 30 and the end date would be imputed as December 31. If the assignment of a missing start or end date conflicts with the available reported data, then the assigned dates will be modified. All modifications will be identified in data listings.

For anti-hypertensive medications, if the start year cannot be determined, this medication should be considered a baseline medication unless the end year is present and prior to the first therapeutic dose of iobenguane I 131.

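### SAP 7.4.1 and 7.4.2(b) credit continuing benefit up to the disposition date without requiring that antihypertensive use be confirmed to that date; the main exposure is reported duration, and the effect on responder status is conditional

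*SAP*

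**What the plan says.** SAP 7.4.2 ends a benefit period at the earlier of two dates. Date (a) is when the reduction is lost, through a lasting dose increase or a lasting new drug. Date (b) is "the date of the subject's last applicable recorded study-related disposition date".

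- **Subjects leaving before Month 12.** "The last participation date is the corresponding disposition date within the 12-Month Efficacy Phase", which the SAP spells out as the "date that the subject withdrew consent, was lost to follow-up, died, withdrew due to disease progression" and so on. SAP 7.4.1 agrees: "the last date for calculation of the duration of benefit is the date of termination in the study".
- **Subjects completing Month 12 still reduced.** "the last applicable disposition date would be the long-term follow-up completion/discontinuation date".

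A responder needs "six consecutive months (i.e., 168 days) duration of sustained" reduction. It must start within the 12-month phase but may finish in long-term follow-up.

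On data collection in years 2 to 5, SAP 4.1 says "data on tumor response, tumor markers and clinical benefit (to month 18 only) will be collected". Protocol 9.1, 11.5.3, 11.5.17 and Appendix VII instead plan recording of concomitant medication until follow-up is complete. Protocol 9.1 and 11.5.17 also limit clinical-benefit data in those years to the time before progression, another anticancer therapy or death.

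SAP 7.4.4 reports maximum duration of benefit (Tables 14.2.1.2A/B, Figure 2) and does not mention censoring.

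**The concern.** Date (a) needs a recorded change of medication. Where records stop, (a) cannot occur and the clock runs on to (b). Any days between the last confirmed medication record and the disposition date are then counted as benefit although nobody knows what the subject was taking.

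Two outputs are exposed. The duration summaries could contain long stretches with no data behind them. A subject could also cross the 168-day line on unconfirmed days and be counted as a responder on the primary endpoint, where the margin is a single subject.

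**Working it through.** **Inputs.** Required duration is 168 days (SAP 7.4.2; six 28-day months, SAP 7). The latest permitted start is 12 calendar months (SAP 7), taken as Day 365. Month 18 is Day 548, the midpoint of Day 518 to 578 (SAP Appendix 1, where that window is listed for tumour response and tumour markers, not for antihypertensive use). Year 5 is about Day 1826 (5 × 365.25). The design values are 0.10 against 0.25, one-sided alpha 0.025, power 0.90, 58 subjects (SAP 6). Success requires a lower 95% Agresti-Coull limit above 0.10 (SAP 7.4.1).

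**1. The plan's own figure.** n = [(1.960·√(0.10·0.90) + 1.282·√(0.25·0.75)) / 0.15]² = [(0.588 + 0.555) / 0.15]² = 58.06. The planned 58 is reproduced.

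**2. Duration.** If collection stops at Month 18 and the period runs to Year 5, the unsupported time is 1826 − 548 = 1,278 days, or 1,278 / 28 = 45.6 of the SAP's months. This is a maximum. It applies to a subject who is still reduced at Month 18 and stays in follow-up to Year 5.

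**3. When responder status is safe.** The latest start plus the requirement is 365 + 168 = Day 533. A medication record at Day 533 or later settles the status of any completer. Day 533 lies before nominal Month 18 (Day 548) but after the earliest day of that window (Day 518).

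**4. Worked cases.** The documents give no observed gaps, so these dates are assumptions.

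| Start | Last medication record | Disposition | Days credited | Days confirmed | Status |
|---|---|---|---|---|---|
| 60 | 203 | Lost to follow-up, Day 230 | 170 | 143 | changes |
| 330 | 365 | Long-term follow-up discontinued, Day 510 | 180 | 35 | changes |
| 365 | 518 | Still in follow-up at Day 533 | at least 168 | 153 | changes |
| 365 | 548 | Still in follow-up | at least 168 | 183 | no change |

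**5. Effect of the SAP 7.9 sensitivity analysis.** It requires the six months to finish inside the 12-month period, so benefit must start by Day 365 − 168 = 197. That removes the second and third cases. The first case stays a responder. The analysis does not touch the duration summaries, and it also drops subjects whose six months were properly confirmed but ended after Month 12.

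**6. The success margin.** With ñ = 58 + 1.96² = 61.84 and p̃ = (x + 1.92) / ñ:

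- x = 11: p̃ = 0.2089; lower limit = 0.2089 − 1.96·√(0.2089·0.7911/61.84) = 0.1076, which passes.
- x = 10: p̃ = 0.1928; lower limit = 0.0944, which fails.

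At a true rate of 0.10, the exact chance of 11 or more is 0.0273. If one non-responder were always miscounted as a responder, it becomes the chance of 10 or more, 0.0605. With 75 subjects the threshold is 13. These figures show what one misclassified subject does, whatever the cause; they do not estimate how often this rule would misclassify.

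**The case against.** The best defence is that antihypertensive use is recorded continuously with dates, not sampled at visits. Protocol 11.5.3 records dose changes and new drugs throughout the study and reviews the list at each visit. Protocol 11.4 requires ongoing contact with the referring physician. Protocol 9.1 and 11.5.17 extend recording through follow-up. For most disposition reasons the date reflects a real contact or event, so medication may well be known up to it. This largely stands, and several stronger readings fail because of it or for related reasons.

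- **A reader might infer that each six-month interval in long-term follow-up is a six-month data gap.** The documents do not support that: a dated change between visits can be captured at the next one. A gap arises only if contact or recording stops, for example with loss to follow-up or death between contacts.
- **A reader might infer that the end-date rule always favours the treatment.** It does not. Protocol 9.8 continues most assessments after early discontinuation, yet the SAP stops the clock at termination, so observed later benefit is discarded.
- **A reader might infer a breach of SAP 7.6, which says** "No imputation of values for missing data will be performed in the primary analysis". That is arguable at most. The same section sets conventions for incomplete medication dates, and an end-of-period rule can be read as another date convention.

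What the defence leaves open is that the SAP's end-date rule does not depend on the recording it assumes, that SAP 4.1 contradicts that recording after Month 18, and that no section says how a loss-to-follow-up date is assigned.

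**Conclusion.** The point holds as a weakness in the end-date rule combined with a conflict between documents. If SAP 4.1 governs, reported durations could include up to about 1,278 days per subject without benefit data. If the Protocol's recording is carried out, little or nothing is unsupported. The documents do not settle which applies.

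The effect on responder status is conditional. It needs a gap before 168 days are confirmed: before Month 12, or for a completer with a late start, no medication record between Month 12 and Day 533. SAP 7.9 covers the long-term follow-up route as a sensitivity analysis but not gaps before Month 12. The number of subjects affected cannot be found from the documents, so it would be wrong to conclude that the primary response rate is inflated. The reason to act is that the decision turns on one subject (11 against 10 of 58) and the repair is cheap. It should be made, but it does not undermine the design.

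**What to change.** - In SAP 7.4.1 and 7.4.2(b), end the credited period at the earlier of the disposition date and the last date on which antihypertensive use was confirmed by visit, contact or dated medication record.
- Count as primary responders only subjects with 168 confirmed days. Report the disposition-date version as a sensitivity analysis.
- In the duration summaries, treat benefit still running at the last confirmed date as censored and use the Kaplan-Meier methods already provided for in SAP 7. Counting it as ended there would bias durations downward.
- Reconcile SAP 4.1 with Protocol 9.1 and 11.5.17. If Month 18 stands, censor duration there.
- State how a loss-to-follow-up date is assigned.

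The cost is SAP wording and a small programming change. A last-confirmed-use date must be derived in long-term follow-up, where assessments follow institutional standard of care and such a date may take some work to obtain. The response rate and durations may come out slightly less favourable.

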7.4.3. Reduction in Use of Antihypertensive Medications for the Per Protocol Set

The primary analysis will be repeated, using only those subjects in the Per Protocol Set.

7.4.4. Other Analyses of Reduction in Use of Antihypertensive Medications

Other analyses of use of antihypertensive medications will include descriptions of the maximum duration of benefit (reduction by at least 50%) beginning during the 12-Month Efficacy Phase, and the proportion of subjects discontinuing all antihypertensive medications completely for at least 6 months beginning during the 12-Month Efficacy Phase. Additional correlations between relative changes in antihypertensive medications and other endpoints may be performed as exploratory analyses. The Spearman correlation coefficient will be reported for any exploratory analyses.

7.4.5. Objective Radiologic Tumor Response

Objective tumor response and overall tumor response will be assessed according to the Response Evaluation Criteria in Solid Tumors (RECIST 1.0)^[2], with the additional category of moderate response, defined below. The RECIST system is described in full in the paper by Therasse et al.^[2], an abbreviated description is provided below.

At baseline, a maximum of 5 lesions per organ and 10 lesions in total are identified on CT/MRI scans as target lesions and recorded and measured. The sum of the longest diameter (SLD) for all target lesions will be calculated and reported as the baseline SLD. The baseline SLD will be used as reference by which to characterize objective tumor response. All other lesions (or sites of disease) should be identified as non-target lesions and should also be recorded at baseline. Measurements of these lesions are not required, but the presence or absence of each should be noted at each follow-up. All bone lesions are considered to be non-target lesions.

Objective tumor response criteria for target lesions are as follows:

Response	Criteria for Response
Complete Response (CR)*	Disappearance of all target lesions
Partial Response (PR)*	Decrease of at least 30% in the SLD, taking as reference the baseline SLD
Moderate Response (MR)*	Decrease of at least 15% but at most 29% in the SLD, taking as reference the baseline SLD
Stable Disease (SD)	Changes do not meet the criteria for CR, PR, MR or PD
Progressive Disease (PD)	Increase of at least 20% in SLD, taking as reference the smallest SLD recorded since treatment started

* To be assigned a status of PR, CR or MR changes in tumor measurements must be confirmed by repeat assessments that should be performed no less than four weeks after the criteria for response are first met.

Objective tumor response criteria for non-target lesions are as follows:

Response	Criteria for Response
Complete Response (CR)*	Disappearance of all non-target lesions
Incomplete Response/Stable Disease (SD)	Persistence of one or more non-target lesion(s)
Progressive Disease (PD)†	Appearance of one or more new lesions and/or unequivocal progression of existing non-target lesions

* To be assigned a status of CR changes in tumor measurements must be confirmed by repeat assessments that should be performed no less than four weeks after the criteria for response are first met.

† For bone lesions, at least two new lesions will be required for a finding of disease progression.

Overall tumor response combines assessment of target lesions and non-target lesions. At each assessment, overall tumor response is that shown in the “Overall Response” column below.

Target Lesions	Non-Target Lesions	New Lesions†	Overall Response
CR*	CR*	No	CR
CR*	Incomplete response/SD	No	PR
PR*	Non-PD	No	PR
MR*	Non-PD	No	MR
SD	Non-PD	No	SD
PD	Any	Yes or No	PD
Any	PD	Yes or No	PD
Any	Any	Yes	PD

* To be assigned a status of PR, CR or MR changes in tumor measurements must be confirmed by repeat assessments that should be performed no less than four weeks after the criteria for response are first met.

† For bone lesions, at least two new lesions will be required for a finding of disease progression.

Radiologic assessments will be listed by target, non-target, and bone (also considered non-target) lesions, for each reviewer, and the case selected by the adjudicator if there was a discrepant result for the overall tumor response. A frequency distribution table will be provided showing, by visit, target, non-target and overall response. This summary will exclude the MR category above (patients with Stable Disease (SD) with a reduction of sum of LD of at least 15% but <30%) as these patients will be classified as SD. A separate summary will be based on the modified RECIST criteria, and will include the MR category. The best overall tumor response using RECIST criteria and best overall tumor response using modified RECIST criteria will also be presented by primary endpoint response status.

The results of the imaging scans including lesion status (e.g., measurable) and tumor size by longest diameter will be listed. A waterfall plot of the greatest decline in the sum of the longest diameters of the target lesions will be presented.

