
13.3.2.2 Secondary Analyses

13.3.2.2.1 Overall Tumor Response per RECIST Criteria

Objective tumor response and overall tumor response will be assessed according to the Response Evaluation Criteria in Solid Tumors (RECIST).⁴³ Tumor size measurements will be obtained by CT or MR at baseline and at 3, 6, 9, and 12 months post-treatment. For each subject, the same modality (CT or MR) and the same technique used for the baseline assessment will be used in all subsequent assessments.

Measurable lesions are lesions that can be accurately measured in at least one dimension with longest diameter ≥ 20 mm using conventional techniques or ≥ 10 mm with spiral CT scan. Non-measurable lesions are all other lesions, including small lesions (longest diameter < 20 mm with conventional techniques or < 10 mm with spiral CT scan), or bone lesions, leptomeningeal disease, ascites, pleural/pericardial effusion, inflammatory breast disease, lymphangitis cutis/pulmonis, cystic lesions, and also abdominal masses that are not confirmed and followed by imaging techniques.

At baseline, all measurable lesions up to a maximum of 5 lesions per organ and 10 lesions in total, representative of all involved organs, should be identified as target lesions and recorded and measured. Target lesions should be selected on the basis of their size (lesions with the longest diameter) and their suitability for accurate repeated measurements (either by imaging techniques or clinically). A sum of the longest diameter (SLD) for all target lesions will be calculated and reported as the baseline SLD. The baseline SLD will be used as reference by which to characterize the objective tumor. All other lesions (or sites of disease) should be identified as non-target lesions and should also be recorded at baseline. Measurements of these lesions are not required, but the presence or absence of each should be noted at each follow-up.

Objective tumor response criteria for target lesions are as follows:

Complete Response (CR)	Confirmed* disappearance of all target lesions
Partial Response (PR)	Confirmed* decrease of at least 30% in the SLD of target lesions, taking as reference the baseline SLD
Moderate Response (MR)	Confirmed* decrease of at least 15% but at most 29% in the SLD of target lesions, taking as reference the baseline SLD
Stable Disease (SD)	Changes do not meet the criteria for CR, PR, MR or PD
Progressive Disease (PD)	At least a 20% increase in the SLD of target

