4.3. Trial Objectives: Secondary

The secondary objectives of this trial are as follows:

- To evaluate the safety of iobenguane I 131 in subjects with malignant pheochromocytoma/paraganglioma, including human radiation absorbed dose estimates to normal organs.
- To assess the proportion of subjects with overall tumor response of CR or PR per RECIST criteria.
- To assess the proportion of subjects with overall tumor response of CR, PR or MR (moderate response, i.e., decrease in the sum of the longest diameters of the target lesions of 15-30%, with no evidence of progressive disease [PD] in non-target lesions) per RECIST criteria.
- To assess status of bone lesions using the Soloway Scale.
- To assess tumor marker response in 24 hr urine and other serum tumor markers associated with pheochromocytoma/paraganglioma.
- To describe changes from baseline in the overall QoL through the EORTC QLQ-C30 questionnaire post-treatment.
- To describe changes from baseline in symptoms using the NIH Quality of Life and Symptoms Questionnaire for Pheochromocytoma and Paraganglioma post-treatment.
- To assess change in use of analgesics and pain medications.
- To describe Karnofsky Performance Status post-treatment.
- To assess overall survival, up to 5 years post-treatment.

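### SAP 7.4.5 ends moderate response at 29% in its table but just below 30% in its text, so a shrinkage between the two is stable disease or moderate response depending on the line followed

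*SAP*

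**What the plan says.** The upper limit of MR is stated in three ways.

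- **Criteria tables.** SAP 7.4.5: "Decrease of at least 15% but at most 29% in the SLD, taking as reference the baseline SLD". Protocol 13.3.2.2.1: "decrease of at least 15% but at most 29% in the SLD of target lesions".
- **SAP 7.4.5, text after the overall-response table.** It points back to the same category ("This summary will exclude the MR category above") and describes those patients as having SD "with a reduction of sum of LD of at least 15% but <30" percent.
- **Objectives.** SAP 4.3 gives a "decrease in the sum of the longest diameters of the target lesions of 15-30" percent, without saying whether the end points are included. The protocol synopsis and Protocol section 8 use the same range.

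The neighbouring categories in the SAP table are fixed. PR is "Decrease of at least 30% in the SLD, taking as reference the baseline SLD". SD is the residual: "Changes do not meet the criteria for CR, PR, MR or PD". Neither document gives a rounding rule for percent change in SLD.

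**The concern.** Percent change in SLD is effectively continuous. A table in which MR stops at 29% and PR starts at 30% leaves a strip one percentage point wide that belongs to neither, and the residual rule sends that strip to SD. The text after the table sends the same strip to MR. Two programmers working from the same section could therefore produce different results from identical data.

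The table read literally is also out of order: a 28.9% decrease is MR, a larger 29.5% decrease is SD, and 30% is PR.

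The proportion with CR, PR or MR is a named secondary objective and endpoint. If the rule is not settled before the data are classified, the choice could be made with knowledge of who lies in the strip.

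**Working it through.** The plan states no figure to reproduce here, so the check applies both rules to the same measurements.

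**Inputs**

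- d = 100 × (baseline SLD − follow-up SLD) / baseline SLD.
- Table rule (SAP 7.4.5 table, Protocol 13.3.2.2.1 table): PR if d ≥ 30; MR if 15 ≤ d ≤ 29; otherwise SD, when neither CR nor PD applies.
- Text rule (SAP 7.4.5, later text): PR if d ≥ 30; MR if 15 ≤ d < 30; otherwise SD, on the same condition.

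**Step 1: classify.** The SLD values are illustrations, not trial data. They assume that confirmation is met, non-target lesions have not progressed and there are no new lesions.

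| SLD, mm | d | Table rule | Text rule |
|---|---|---|---|
| 120 to 85 | 35/120 = 29.17% | SD | MR |
| 85 to 60 | 25/85 = 29.41% | SD | MR |
| 95 to 67 | 28/95 = 29.47% | SD | MR |
| 44 to 31 | 13/44 = 29.55% | SD | MR |

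At d = 29.0 or less, and at d = 30.0 or more, the two rules agree. They differ only for 29 < d < 30.

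**Step 2: test rounding as an explanation.** Suppose d were rounded to a whole percent before the table is applied (an assumption). Then 29.17% becomes 29 and is MR, but 29.55% becomes 30 and is PR. At the lower limit, 14.9% becomes 15 and is MR. Rounding gives a third classification that matches neither line.

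**Step 3: trace the outputs.**

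- Primary endpoint: based on antihypertensive medication, so not affected.
- CR/PR proportion: a value in the strip is below 30% under both rules, so not affected.
- Standard RECIST table: SAP 7.4.5 counts MR as SD there, so SD either way.
- Modified-RECIST summaries, including the one by primary endpoint status, and the CR/PR/MR proportion: these can change.

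**Step 4: size per subject.** The documents do not give the size of the Full Analysis Set. The planned evaluable number (58) and planned enrolment (75) serve as an assumed range: 1/58 = 1.7 percentage points and 1/75 = 1.3 percentage points.

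**The case against.** The best defence is that the SAP largely explains itself. The later text refers to the category above and gives it a continuous limit that meets PR exactly, so the 29 in the table can be read as whole-percent shorthand for anything short of PR. That is probably the intention. It does not settle the matter, because no rounding rule is stated, literal rounding turns part of the strip into PR, and the table is the natural place to code from.

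It can also be said that the SAP's listing of response and SLD by reviewer and its waterfall plot would expose any such case, and that the Imaging Charter, which is not among the documents, may fix reader practice. Both are fair. Neither reconciles the two lines, and finding a case in the listings would mean choosing the rule afterwards.

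Three stronger readings are tempting and should not be drawn.

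- **That about one moderate responder in 15 is lost.** One percentage point is 1/15 = 6.7% of the 15-30% range if decreases are spread evenly. That is an assumption, and it concerns single measurements. MR needs confirmation at least four weeks later, scans are scheduled at Months 3, 6, 9 and 12, and best overall response is reported. A subject in the strip at one visit may be MR or PR from other visits. Conversely, under the table rule a second scan in the strip might fail to confirm an earlier MR. No rate per subject follows.
- **That objective response in the usual sense is at risk.** Both rules keep the strip outside PR.
- **That the 15-30% in the objectives makes a 30% decrease ambiguous in the analysis.** The ranges touch at exactly 30%, but both operational tables assign 30% to PR. This is loose wording to tidy, not a competing rule.

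**Conclusion.** The inconsistency is real and the table rule is wrong as written: followed literally, it scores a decrease above 29% and below 30% as SD, while the text of the same section scores it as MR. The consequence is confined to the CR/PR/MR proportion and the modified-RECIST summaries. Trial success does not depend on either, since it rests only on the antihypertensive endpoint.

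The point is minor. It may affect no subject at all. Each reclassified subject is worth 1.3 to 1.7 percentage points, on the assumption that the denominator lies between 58 and 75.

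**What to change.** In the SAP 7.4.5 criteria table, define MR as a decrease in SLD of at least 15% and less than 30% from baseline, calculated on the unrounded percentage. Make SAP 4.3 agree. This adopts the limit that the later text of 7.4.5 already states ("reduction of sum of LD of at least 15% but <30" percent). It closes the gap, removes the overlap at 30% and leaves PR unchanged.

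Add a sentence to the SAP recording that this supersedes the wording in the protocol synopsis, Protocol section 8 and Protocol 13.3.2.2.1. Protocol 13.5 provides for changes to the protocol's analysis to be documented in the final SAP. The three protocol places can be corrected at the next amendment, if there is one. An amendment for this alone is hard to justify, because Protocol 15.2 requires signatures and IRB submission, and SAP 4.1 reports that enrolment was completed in December 2015.

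The cost is two edits and one recorded change in the SAP, preferably before database lock. No new data or reads are needed.
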